4.4.3 Rationale for Evaluation Endpoints Selection

Rationale for safety endpoint selection: The safety indicators set for this study aligns with the NMPA requirements, which state, "The observation indicators include at least the following: , related stroke events, and clinical follow-up of deaths, strokes, and disease-related symptoms within 6 months". The recommendation of *Chinese guidelines for the treatment of intracranial aneurysms with flow divertor* is that the vast majority of occlusion of aneurysms after FD implantation occurs within 12 months after treatment. The incidence and severity of AEs/SAEs meet the relevant requirements for safety indicators in the *Guidelines for Clinical Study Design of Medical Devices*.

Rationale for efficacy endpoints selection: This clinical study is conducted in accordance with NMPA requirements to evaluate the long-term follow-up safety information of FRED following its market release. The efficacy indicators set for this study aligns with the NMPA requirements, which state, "The observation indicators include at least the following: technical success rate, re- sheathing performance, perioperative period". In addition, the observational device FRED features a finer mesh design compared to conventional intracranial stents, which allows it to cover the aneurysm neck, redirect blood flow, and promote blood stasis within the aneurysm, leading to thrombus formation and an increased aneurysm occlusion rate. To evaluate the efficacy of the observational device, the clinical study selected the aneurysm occlusion rate as the efficacy endpoint.

4.5 The Data Collection Schedule

The data collection schedule is described in

Table 4-3 Data Collection Plan

Baseline	Treatment*	Follow-Up Information**

Demographic Information¹Medical History²Physical Examination³Imaging findings⁴Modified Rankin ScaleAneurysm Information⁵Laboratory Examination⁶Information of antiplatelet function test result: platelet aggregation test/ Thromboelastographic (TEG)Information of anti-coagulation and anti-platelet medication⁷	
Using Information of DeviceInformation of ProcedureStrokeMortalityAE/SAEO'Kelly-Marotta(OKM) GradeRaymond-Roy GradeTechnical SuccessRe-sheathing Performance	
Physical Examination⁴Information of anti-coagulation and anti-platelet medication⁷Image dataLesion-Related ComplicationStrokeMortalityAE/SAE⁸O'Kelly-Marotta(OKM) GradeRaymond-Roy gradeModified Rankin Scale

Notes:

1. Demographic Information including: birth date, sex, history of smoking and drinking, ethnicity, diagnosis.
2. Medical History: Past medical history: including current medical conditions (high blood pressure, diabetes, etc.), history of cranial and neurological related surgeries, hemorrhagic stroke.

3. Physical Examination: neurological physical examination.

4. Image data collection, per standard of care (e.g., DSA, MRA, CTA) can be applied.

5. Based on CTA .

6. Laboratory Examination: Blood routine (red blood cell count, hemoglobin white blood cell count, neutrophil count, lymphocytes count, platelet count), coagulation test [Prothrombin Time (PT), Activated Partial Thromboplastin Time (APTT), Thrombin Time (TT) and Fibrinogen (FIB) International standardized ratio (INR)]. Only clinically significant abnormal results were recorded.

7. Information on anti-coagulation and anti-platelet medication: drug name, dosage and frequency of administration are needed.

*. If the same patient received other surgical treatments using observational device within the data collection time frame, only the first treatment data was selected as the baseline data, and the follow-up time was calculated at this point. The remaining surgical treatments were recorded as "concomitant surgery".

** Each patient may have multiple follow-up information, all of which should be recorded and collected. The collected follow-up data will be divided according to the following follow-up points: 30 days after surgery, 3 months after surgery, 6 months after surgery, and 1 year after surgery, according to the principle of closest approach.

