4.4.2 Efficacy Endpoint

(1) Imaging Evaluation of a Target Aneurysm (O' Kelly-Marotta, (OKM))

Definition: Based on the evaluation of imaging results, the treatment of aneurysms was classified according to the following criteria. Digital Subtraction Angiography (DSA), Magnetic Resonance Angiography (MRA), or Computed Tomography Angiography (CTA) are acceptable, and it is recommended base CTA. The purpose of imaging follow-up information collection is to observe the effect of on the long-term closure of the aneurysm after treatment. Complete closure of the aneurysm would be associated with increased safety.

- No filling
- Entry remnant (<5%)
- Subtotal filling (5%~95%)
- Total filling (>95%)

The observational device with the blood flow and the aneurysm gradually closes. The evaluation results of different follow-up nodes were counted, and the time interval between the date of surgery and the aneurysm occlusion is collected.

(2) Adequate Occlusion Rate of Target Aneurysm

Definition: Adequate Occlusion is defined as Raymond-Roy Grade I or Grade II on imaging evaluation of the target aneurysm ^[5]. If the Raymond-Roy grade reaches Grade I at any evaluation point, no further imaging information will be collected. Imaging results obtained via Digital Subtraction Angiography (DSA), Magnetic Resonance Angiography (MRA), or Computed Tomography Angiography (CTA) is acceptable. The imaging results will be evaluated following the routine procedures of the clinical research institution. The post-procedure recanalization of the aneurysm is graded according to the following classification. Please refer to **Error! Reference source not found.** for Raymond-Roy Classification Standards.

Table 4-1 Raymond-Roy Classification Standards

Grade	Description
Grade I	Complete occlusion (no contrast filling in the aneurysm sac or neck)
Grade II	Neck remnant (contrast filling in the aneurysm neck but not the sac)
Grade III	Residual sac (contrast filling in the aneurysm sac)

Occlusion Rate of Target Aneurysm refers to the proportion of patients judged to be Grade 1 or Grade 2 in the total number of patients.

(3) Technical Success Rate

Definition: Technical success is defined as successful stent placement and meet following criteria:

- Stent fully cover the aneurysm neck
- Good wall apposition
- Perfusion of the parent artery
- Retention of contrast agent within the aneurysm.

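### Later FRED procedures are logged without saying whether they retreated the target aneurysm, so occlusion reached only after retreatment enters the occlusion rate unmarked

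*Protocol*

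**What the plan says.** The asterisked note under Table 4-3 (Protocol, Section 4.5) applies "If the same patient received other surgical treatments using observational device within the data collection time frame". It then fixes two things:

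- **Time origin.** "only the first treatment data was selected as the baseline data, and the follow-up time was calculated at this point".
- **Label.** "The remaining surgical treatments were recorded as" concomitant surgery.

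The next note says "Each patient may have multiple follow-up information, all of which should be recorded and collected". Records are sorted to "30 days after surgery, 3 months after surgery, 6 months after surgery, and 1 year after surgery, according to the principle of closest approach".

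Section 4.4.2 (2) states the endpoint: "Adequate Occlusion is defined as Raymond-Roy Grade I or Grade II on imaging evaluation of the target aneurysm". The rate is then given as a share of all patients: "Occlusion Rate of Target Aneurysm refers to the proportion of patients judged to be Grade 1 or Grade 2". The same section ends image collection once Grade I is seen at any evaluation. Section 4.4.2 (1) collects the interval from surgery to occlusion. Section 5.2 analyses every eligible patient.

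**The concern.** A later FRED procedure can mean two different things. It may treat another aneurysm, which has no bearing on occlusion of the target. Or it may treat the target again because the first treatment did not close it. The note gives both the same label and attaches no consequence to either. It does not mention coils, another stent or clipping used on the target later.

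Sections 4.3.3 and 4.3.4 do not ask which aneurysm a later procedure addressed. Retreatment is not among the safety or efficacy endpoints in Section 4.4. An elective readmission for retreatment might also be missing from the SAE tables, because Section 10.2.1 excludes planned hospitalization for a pre-existing condition.

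The interpretation of the main efficacy measure is at stake. Section 4.4.3 chooses the aneurysm occlusion rate to evaluate the device. A reader of the report could not tell how much of that rate was reached after the initial treatment alone. If the information is not abstracted now, no later analysis plan can recover it.

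**Working it through.** **1. No figure to reproduce.** The protocol states no sample size, expected occlusion rate or retreatment rate. The check is therefore to follow one patient through the rules and then to illustrate the size.

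**2. One hypothetical patient.**

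| Time from first FRED | Event | Treatment under the protocol |
|---|---|---|
| Month 8 | Image, Grade III | Nearest follow-up point is 6 months (2 months away, against 4 to the 1-year point) |
| Month 9 | Second FRED at the target | Labelled concomitant surgery; clock unchanged |
| Month 15 | Image, Grade I | Nearest listed point is 1 year; imaging collection ends |

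Section 4.5 lists no point after 1 year and gives no outer window. As written, the patient is not occluded at 6 months and is adequately occluded at 1 year. The time to occlusion is 15 months from the first surgery. Nothing in the endpoint marks the second device.

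**3. Size.** Let *p* be the proportion with Grade I or II after the initial treatment alone, *r* the share of the remaining patients who are retreated at the target, and *s* the share of those who then reach Grade I or II. All three are assumptions.

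- Counted rate = *p* + (1 − *p*) × *r* × *s*
- Excess over the initial treatment alone = (1 − *p*) × *r* × *s*

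| *p* | *r* | *s* | Counted rate | Excess (points) |
|---|---|---|---|---|
| 90% | 10% | 50% | 90.5% | 0.5 |
| 80% | 10% | 50% | 81.0% | 1.0 |
| 80% | 30% | 50% | 83.0% | 3.0 |
| 80% | 50% | 80% | 88.0% | 8.0 |
| 60% | 50% | 80% | 76.0% | 16.0 |

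Over *p* = 60% to 90%, *r* = 10% to 50% and *s* = 50% to 80%, the excess runs from 0.5 to 16 points.

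For the middle row with an assumed 200 patients, the exact binomial intervals that Section 5.3.4 specifies are:

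- as counted: 166/200 = 83.0% (95% CI 77.1% to 87.9%)
- initial treatment alone: 160/200 = 80.0% (95% CI 73.8% to 85.3%)

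**4. Why this is an upper bound.** The formula assumes that no retreated patient would have closed without the second procedure. Section 4.4.2 describes closure as gradual, so some would have. A patient already at Grade II when retreated adds no excess, because that patient already met the definition.

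**5. Plausibility of large values.** For the rate to fall from 85% as counted to 75% after the initial treatment alone, 10 of every 25 initial failures must be retreated and then occlude. That means *r* × *s* = 0.10 / 0.25 = 0.40, for example 50% × 80%, the top corner of the assumed range.

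**The case against.** A reader might infer that the protocol declares occlusion after retreatment to be a success of the first device. It does not say so. The note fixes a time origin and a label, and starting the clock at the first implant is sound because it counts each patient once. The scoring result comes from the absence of any retreatment condition. The SAP, which is not shown, could use the label to censor patients or count them as failures.

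A reader might also call the rate simply biased. The objective is the efficacy of FRED in treating aneurysms, and occlusion regardless of retreatment is a legitimate quantity. Preferring occlusion without retreatment is a choice of question.

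Three further points carry weight:

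- Section 2.3.8 lists a pre-existing stent at the target as a contraindication, so repeat FRED at the same site may be rare. Section 4.2.2 sets no exclusions, however, and other-device retreatment is a separate route.
- Safety is less affected than it looks. Keeping events after a second procedure in the rates is conservative, and the CEC judges relation to device or procedure.
- Scoring every retreated patient as a failure would misclassify one already at Grade II.

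All of this narrows the point, but the data-capture gap remains. An SAP can reclassify patients only if someone recorded that the later procedure treated the target, when, and with what. The protocol does not ask for that.

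**Conclusion.** The concern holds in a limited form. Followed as written, Sections 4.4.2 and 4.5 let occlusion reached only after target retreatment into the occlusion rate and the time to occlusion without a mark, and no endpoint reports retreatment.

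Taken as the result of the initial treatment, the rate is overstated by at most the share of patients who reach Grade I or II only after retreatment. The documents give no value for that share. The 0.5 to 16 points rest wholly on assumed inputs, and the effect is zero if no target is retreated.

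The documents do not support the stronger claims that the protocol credits the first device by rule, that the overstatement equals the retreatment rate, or that the safety rates are distorted. The study is descriptive with no success criterion (Section 5.6), so no pass or fail decision is affected. What suffers is the interpretation of the efficacy result.

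**What to change.** Amend the asterisked note in Section 4.5 and align Section 4.4.2:

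- For any later procedure, with any device or by surgery, record the date, the device and whether it treated the same target aneurysm. Keep the concomitant surgery label for other aneurysms.
- Report the target-aneurysm retreatment rate.
- Report adequate occlusion without target retreatment alongside the rate regardless of retreatment. For the former, a patient retreated for inadequate occlusion counts as not occluded by the initial treatment from that date. A grade documented before retreatment stands at its own visit. Handle time to occlusion in the same two ways.
- Flag safety events after a second procedure and keep them in the overall rates.

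The cost is one or two eCRF fields and a short text change. One of the two reported occlusion rates may be slightly lower. Patient care is not affected.

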The technical success rate refers to the proportion of technically successful patients in the total number of patients.

(4) Re-sheathing performance

Definition: During procedure, the observational device can be retrieved / re-sheathed into the microcatheter and re-deployed at the desired target location or removed completely from the patient. But it must not be re-deployed more than three times. Re-sheath performance refers to the retrieving and re-deploying of observational device recorded during the procedure. Information such as the number of recoveries and the number of re-sheathings, the success rate of re-opening and other information are recorded to evaluate the re-sheath performance of the observational device.

(5) Modified Rankin Scale (mRS) Change from Baseline

Definition: At different follow-up, the modified Rankin score changed from the baseline.

The modified Rankin (mRS) score was used to evaluate the improvement of neurological function. The modified Rankin score assesses the ability to live independently in patients with Neurological disease [6]. There are 7 levels of this score, 0 points represent no symptoms of disability, higher scores mean worse prognosis of patients, and 6 points represent death, See the table below for detailed scores.

Table 4-2 Modified Rankin Scale (mRS)

Score	Patient Condition
0	No symptoms of disability
1	Minor symptoms but no significant deficits; capable of all activities and work
2	Mild disability; unable to participate fully in previous activities but can live independently
3	Moderate disability; requires assistance but can walk independently
4	Moderate to severe disability; unable to walk independently, cannot live alone, requires some care
5	Severe disability; bedridden, incontinent, requires constant care
6	Death

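### The 1-year follow-up point in section 4.5 has no upper limit and nothing after it, so a record made years later can be reported as 1 year

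*Protocol*

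**What the plan says.** The second footnote to Table 4-3 in protocol section 4.5 governs the follow-up column, which includes OKM grade, Raymond-Roy grade and mRS. It states "Each patient may have multiple follow-up information, all of which should be recorded and collected", and then divides the collected data among "30 days after surgery, 3 months after surgery, 6 months after surgery, and 1 year after surgery, according to the principle of closest approach". It gives no lower or upper bounds, and no other section adds bounds or a later point.

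Three efficacy endpoints in section 4.4.2 draw on this column:

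- **OKM imaging.** "The purpose of imaging follow-up information collection is to observe the effect of on the long-term closure of the aneurysm after treatment" (section 4.4.2(1)). The same paragraph says "The evaluation results of different follow-up nodes were counted, and the time interval between the date of surgery and the aneurysm occlusion is collected".
- **Adequate occlusion.** This is "the proportion of patients judged to be Grade 1 or Grade 2 in the total number of patients", with no visit named. Section 4.4.2(2) also states "If the Raymond-Roy grade reaches Grade I at any evaluation point, no further imaging information will be collected".
- **mRS.** "At different follow-up, the modified Rankin score changed from the baseline" (section 4.4.2(5)).

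Section 3 gives the objective as long-term safety and efficacy. Sections 4.1 and 5.4 run implantation and data collection from May 2023 to May 2027.

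**The concern.** A nearest-point rule closes each window at the midpoint to the next point. The last point has no next point, so its window never closes. Patients treated early in the study can have records well beyond one year, and the only place the rule offers for them is the 1-year class. A patient whose only late image was taken at month 36 would count in the 1-year column.

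Two things are at stake. The first is whether the 1-year label is true: the study is descriptive, so a reader will take a 1-year OKM or mRS table at face value. The second is the fit with the objective: records from years 2 to 4 are collected, but no by-visit table shows them as such.

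**Working it through.** The protocol gives no figure to reproduce. The check is calendar arithmetic followed by an illustration on assumed inputs.

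**1. Where the 1-year class starts.** Take the four points in section 4.5 as days 30, 91, 183 and 365. Nearest-point boundaries are the midpoints:

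- (30 + 91)/2 = 60.5
- (91 + 183)/2 = 137
- (183 + 365)/2 = 274

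Other month-length conventions put the last boundary between day 270 and day 274.

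**2. Where it ends.** The rule sets no end, so the limit is the longest possible follow-up. From 1 May 2023 to 31 May 2027 is 1,491 days, and 1,491/30.4375 = 49.0 months. From 31 May 2023 to 1 May 2027 is 1,431 days, or 47.0 months. Both assume that data are cut at the end of the last period in section 5.4. The study duration of about 36 months in section 4.1.2 does not cap one patient's follow-up in a retrospective design.

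**3. Width.** The 1-year class can span 1,491 − 274 = 1,217 days, which is 1,217/1,491 = 82% of the longest possible follow-up.

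**4. Who is affected.** Take the reading kinder to the plan, in which the single record nearest each point is used. A late record then enters the 1-year class only when the patient has no nearer one. Table 4-3 collects images per standard of care, so such patients are foreseeable. Because imaging collection stops at Grade I, late images come only from aneurysms not yet at Grade I. mRS has no such stop.

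**5. Possible size on Grade I (all inputs assumed).** Of 100 patients, c are at Grade I before month 9 and are carried forward. Of the rest, one third are at Grade I by month 12 and one half by month 36. With c = 70 this is 10 of 30 at month 12, then 2 more at month 24 and 3 more at month 36, giving 15 of 30. A share s of the patients still open have only a month-36 image, independently of outcome.

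Shift in the 1-year Grade I rate = (100 − c) × s × (1/2 − 1/3), in percentage points:

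| c | s = 0.10 | s = 0.50 |
|---|---|---|
| 50 | 0.83 | 4.17 |
| 70 | 0.50 | 2.50 |
| 80 | 0.33 | 1.67 |

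For c = 70 the true month-12 rate is 70 + 10 = 80%, and the reported rate would be 80.5% to 82.5%.

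**6. Possible size on adequate occlusion (Grade I or II).** Keep c = 70 and suppose the 20 patients not at Grade I at month 12 are 10 Grade II and 10 Grade III. If none to half of the Grade III improve by month 36, the shift is 10 × s × (0 to 0.5). That is 0 to 0.5 points for s = 0.10 and 0 to 2.5 points for s = 0.50, so it may be nil.

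Steps 5 and 6 allow only improvement. Later worsening would push the other way, so the direction is not known.

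**The case against.** **Window bounds usually belong in the SAP.** This is the strongest objection, since section 5.3.1 leaves detailed analysis to a separate SAP. It would succeed if section 4.5 were silent. But section 4.5 itself fixes the data, the points and the allocation rule, and it does not refer onward, as section 5.5 does for missing values. A SAP that closed the window would be departing from a stated rule.

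**Twelve months is a reasoned horizon.** Section 4.4.3 says that most occlusion after flow diversion happens within 12 months, and the protocol never defines long-term. That supports having a 1-year point. It does not support putting a year-3 record under that label. It is also fair that late imaging columns would be sparse and selected, because of the Grade I stop. That does not apply to mRS.

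**Late closure is not lost.** This stands: the surgery-to-occlusion interval is collected and keeps its actual length.

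A reader might also infer more than the text supports:

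- *That a patient's last image will stand for 1 year.* This would give a larger distortion, but no section states a last-image rule, and closest approach points the other way.
- *That all efficacy results are affected.* Only OKM and mRS are expressly reported by follow-up point. Adequate occlusion names no visit, and technical success and re-sheathing are assessed immediately after the procedure.
- *That late deaths will appear as 1-year mRS scores.* Section 4.4.2(5) says "higher scores mean worse prognosis of patients, and 6 points represent death", but this defines the scale. Nothing says that deaths are entered as follow-up scores, and mortality is a separate endpoint with its own date.

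**Conclusion.** The point holds in a limited form. Following section 4.5 as written, a record from about day 274 to as late as month 49 can be reported as 1 year, at least when the patient has no nearer record. By-visit OKM and mRS results are exposed, and so are Raymond-Roy results if they are tabulated by follow-up point. The long-term objective and the imaging purpose have no by-visit result after 1 year.

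The boundary and the maximum follow-up are firm, given a cut at the end of May 2027. The size is not: 0.3 to 4.2 points on Grade I and possibly nothing on Grade I or II, all on assumed closure rates and shares of late-only patients. No size is estimated for mRS. Safety proportions are taken over all patients and do not depend on the allocation. This should be corrected, but it does not undermine the study.

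**What to change.** In section 4.5:

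- Give the 1-year window an upper bound close to its label, for example day 275 to 455 (365 ± 90 days).
- Use one record per patient and window, the one closest to the target day.
- Report later records in one or more separate classes labelled with their day range, and tabulate actual days from the procedure. For example, use day 456 to 912 around 2 years and day 913 to the data cut for 3 years or later; the split is the midpoint (730 + 1,095)/2 = 912.5.
- In the late imaging columns, count patients already at Grade I separately, for example as Grade I at last image, because no later images are collected for them.

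The cost is a few sentences and one or two extra table columns. No new collection is needed, since section 4.5 already records all follow-up. The downside is fewer patients in the 1-year column: those with only a late record become missing there and fall under section 5.5. The late imaging columns will be sparse and selected.
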